8.1.4. Demography and Medical History

8.1.4.1. Demographics and General Medical History

Demographic data and general medical history will be collected at screening by the investigator or qualified designee and will include date of birth, race, ethnicity, medical and surgical history, and current illnesses. Medical history will include relevant medical or surgical treatment within the last year that are considered to be clinically significant by the investigator.

8.1.4.2. Disease Characteristics and Treatment History

A disease-targeted medical and treatment history will be collected at screening. A detailed history of prior medications use related to HS in the year before screening will be also be collected, as well as response to each treatment and reason for discontinuation.

8.2. Efficacy Assessments

An example of the lesion count worksheet is provided in Appendix D and will be used for assessment of Hurley Stage, HiSCR, modified Sartorius scale, and (see Section 8.5.3). It includes assessment of 12 anatomic regions: left/right axilla, left/right sub/inframammary area, intermammary area, left/right buttock, left/right inguino-crural fold, perianal area, perineal area, and other areas. Additionally, the need for rescue lesional treatment, including number of interventions, will be documented in this worksheet.

8.2.1. Hurley Stages of Hidradenitis Suppurativa

Hurley Stages of HS are defined in Table 8. The investigator will determine the Hurley Stage in each affected anatomical region at the designated study visits listed in Table 3. If more than 1 stage is present in a region, the worst stage in each region should be documented. The participant is assigned Hurley Stage corresponding to the Hurley Stage of his or her worst involved anatomic region.

Table 8: Hurley Stages of Hidradenitis Suppurativa

Stage	Description
Ι	abscess formation (single or multiple) without sinus tracts and cicatrization
II	recurrent abscesses with tract formation and cicatrization; single or multiple, widely separated lesions
III	diffuse or near-diffuse involvement or multiple interconnected tracts and abscesses across the entire area

8.2.2. Hidradenitis Suppurativa Clinical Response (Abscess and Inflammatory Nodule Count)

An HiSCR is defined as at least 50% reduction in AN count with no increase in abscess count and no increase in draining fistula (see definition below) count relative to baseline at each visit (see Appendix D; Kimball et al 2016).

A fistula is a pathologic passageway connecting to the skin surface from dermis or subcutaneous tissue. Draining fistulas are fistulas that drain serous or purulent fluid, either spontaneously or by gentle palpation.

8.2.3. Modified Sartorius Scale

The modified Sartorius scale is a measure of the severity of HS (see Appendix D and Appendix E; Sartorius et al 2003).

Points are given as follows for each body area: 2 points for each nodule (both inflammatory and non-inflammatory); 4 points for each abscess; 4 points for each fistula (both draining and non-draining); 1 point for each scar; 2 to 6 points for the longest distance between 2 lesions or 0 points if no lesions; and 6 points if lesions are not separated by normal skin or 0 points if lesions are separated by normal skin. The "other area" only with the highest modified Sartorius scale at baseline will be calculated, and the same area should be evaluated throughout the study. The total modified Sartorius scale score is the sum of the 12 anatomic region scores.

8.2.4. Need for Rescue Lesional Treatment

The need for lesional rescue treatment will be recorded as a measure of efficacy.

In the event of an acutely painful lesion that requires immediate intervention, investigators will have the option to perform protocol-allowed interventions. Two types of interventions are permitted: injection with intralesional triamcinolone acetonide suspension (up to 30 mg in total at the same visit) and/or incision and drainage. If incision and drainage is performed, participants should continue using the same over-the-counter antiseptic as previously. New systemic and topical therapies following incision and drainage, including antibiotics, are prohibited. Concomitant use of wound care dressings is allowed as described in Section 6.6.2.4. Participants should continue using any oral and topical therapies during the study, consistent with the allowances and restrictions described in Section 6.6.2.

From Day 1 through Week 8, an intervention can occur on a maximum of 2 different lesions at the same visit or on the same lesion at 2 different study visits. The same lesion cannot be treated 2 times during the same visit. If participants require more than 2 interventions before Week 8, then study drug will be discontinued for those participants.

Study procedures must be performed before any interventions. Any lesion undergoing an intervention will be documented in the lesion count worksheet (see Appendix D). The site will be required to count any lesion that undergoes an intervention as permanently present from the date of the intervention, and must account for it in the source and on the appropriate eCRF.

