2.2.1. Scientific Rationale for Study Design

Recent literature suggests that the main cytokines involved in HS pathogenesis are IL-1β, IL-17, IL-23, IL-10, and, to a lesser extent, TNF-α (Kelly and Prens 2016). The expression and/or activity of these cytokines is mediated at the intracellular level through JAK-STAT signaling, and primarily JAK1 inhibition (see Section 2.1.3).

In the current study, the clinical safety and efficacy of 15 mg QD INCB054707 will be evaluated in adult participants with moderate to severe HS. The primary endpoint is to evaluate the safety and tolerability of INCB054707.

For participants experiencing bothersome symptoms related to either rapid abscess formation or secondary infection at the diseased sites, appropriate rescue treatments will be offered to immediately evacuate pus (incision and drainage), alleviate the level of inflammation (intralesional triamcinolone), or control infection (see Sections 6.6.2 and 8.2.4)

It is expected that the outcome of this study will be instrumental in informing the dose-ranging Phase 2b study.

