6.6.2. Permitted Medications and Procedures

6.6.2.1. Antibiotic Therapy

After Week 4, if a participant experiences signs or symptoms indicative of an infection at an HS site (eg, fever and local/regional lymphadenopathy), the following antibiotic therapy may be initiated without interruption of study drug administration:

• Amoxicillin 500 mg/clavulanic acid 125 mg, 2 tablets, 3 times daily for 3 days

In participants for whom amoxicillin is contraindicated, the investigators should consult with the sponsor or designee to discuss alternative treatment options.

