6.6.3. Prohibited Medications and Procedures

The following medications are prohibited for all participants in the study:

- JAK inhibitors, systemic or topical (eg, ruxolitinib, tofacitinib, baricitinib, filgotinib, lestaurtinib, and pacritinib).
- Adalimumab or any other TNF- α treatment or any experimental treatments.
- Systemic immunosuppressive or immunomodulating drugs (eg, oral or injectable corticosteroids, methotrexate, cyclosporine, and azathioprine).
- Systemic and/or biologic therapies with potential therapeutic impact for HS.
- Surgical, laser, or IPL intervention in area with HS lesion, except as specified in Section 8.2.4 for rescue lesional treatment.
- Systemic anti-infectives (eg, antibiotics, antivirals, and antifungals), except as described in Section 6.6.2.1 for antibiotic therapy, or topical anti-infectives on HS lesions.
- Conventional therapies with potential therapeutic impact for HS.
- Topical antiseptic washes, creams, soaps, ointments, gels, and liquids containing antibacterial agents to treat HS, except those listed in Sections 6.6.2.3 and 6.6.2.4.

- Potent systemic CYP3A4 inhibitors or inducers or fluconazole.
 Note: Topical agents with limited systemic availability are permitted.
- Concomitant uses of P-gp inhibitors and inducers (see Appendix C) need to be consulted with the medical monitor.
- Live vaccines (during the study and within 6 weeks after EOT).

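### Protocol 8.2.4 and 6.6.2.1 give opposite antibiotic rules for a drained lesion that shows infection after Week 4, and the rescue stop rule counts interventions without a stated unit

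*Protocol*

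**What the plan says.** **Antibiotics.** Protocol 8.2.4, on rescue treatment, states: "New systemic and topical therapies following incision and drainage, including antibiotics, are prohibited". No end date and no exception for infection are attached.

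Protocol 6.6.2.1 sets a different rule. Its trigger is "After Week 4, if a participant experiences signs or symptoms indicative of an infection at an HS site", and in that case "the following antibiotic therapy may be initiated without interruption of study drug administration". Drained sites are not excluded. The list of prohibited medications in 6.6.3 bars systemic anti-infectives "except as described in Section 6.6.2.1 for antibiotic therapy, or topical anti-infectives on HS lesions"; it does not mention the restriction in 8.2.4. The design rationale in 2.2.1 gives three purposes of rescue treatment, the last being "or control infection (see Sections 6.6.2 and 8.2.4".

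**Combined procedures.** Protocol 8.2.4 permits two types of intervention: "injection with intralesional triamcinolone acetonide suspension (up to 30 mg in total at the same visit) and/or incision and drainage". The next paragraph limits rescue from Day 1 through Week 8 to two lesions at one visit or one lesion at two visits. It then adds "The same lesion cannot be treated 2 times during the same visit", followed by the stop rule: "If participants require more than 2 interventions before Week 8, then study drug will be discontinued for those participants".

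**Analysis.** SAP 7.2 lists two rescue endpoints: the proportion of participants who needed rescue, and the number of interventions. SAP 7.1.4 repeats the rule for recording a treated lesion. Neither section gives a unit for the count.

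**The concern.** An investigator with a drained lesion that shows infection after Week 4 finds permission to start an antibiotic in one section and a prohibition in another. Both cannot be followed. The study is multicenter, so sites may resolve this differently, and the participants concerned are taking a JAK1 inhibitor. A choice that follows one section can be recorded as a deviation under the other.

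The unit of an intervention matters for a different reason: it feeds a mandatory stop of study drug. Two sites that perform the same procedures on the same lesions could reach different decisions on stopping, and could enter different numbers for the intervention endpoint.

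**Working it through.** **1. Antibiotics.** Take a participant who has had incision and drainage and who, after Week 4, shows signs of infection at the drained site.

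| Section | Does it apply? | Result |
|---|---|---|
| 6.6.2.1 | Yes: after Week 4, infection at an HS site | Named antibiotic may be started |
| 6.6.3 | Yes: the exception for 6.6.2.1 is met | Not prohibited |
| 8.2.4 | Yes: a new antibiotic following drainage | Prohibited |

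No section states an order of precedence. One sentence in 8.2.4 does refer to the allowances and restrictions of 6.6.2, but its subject is therapies that participants keep using. An antibiotic started for a fresh infection is a new therapy, so that sentence does not settle the matter.

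Before Week 4 the three sections agree. Section 6.6.2.1 has not begun to apply, 6.6.3 has no other exception for systemic anti-infectives, and 8.2.4 prohibits new antibiotics after drainage.

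**2. Counting interventions.** The text of 8.2.4 supports two units. It calls injection and drainage two types of intervention, which suggests one count per procedure. It frames its limits by lesion and visit, which suggests one count per lesion per visit. The stop rule applies when the count exceeds 2.

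| Scenario | Per lesion-visit | Per procedure | Stop rule |
|---|---|---|---|
| One lesion, one visit, both procedures | 1 | 2 | Continue under both |
| Two lesions, one visit: both procedures on one, one on the other | 1 + 1 = 2 | 2 + 1 = 3 | Continue or stop |
| Two lesions, one visit, both procedures on each | 1 + 1 = 2 | 2 + 2 = 4 | Continue or stop |
| One lesion, two visits, both procedures each time | 1 + 1 = 2 | 2 + 2 = 4 | Continue or stop |

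Whether these scenarios can arise within the protocol depends on the same-lesion rule:

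- If both procedures on one lesion are one treatment and one intervention, they are allowed and the lesion-visit column applies.
- If they are two treatments, the same-lesion rule bars them, and no compliant participant reaches 3 or 4.
- If they are one treatment for the same-lesion rule but two interventions for the stop rule, they are allowed and the per-procedure column applies.

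**3. What the count touches.** A participant with 1, 2, 3 or 4 interventions has had rescue in every case, so the proportion needing rescue does not move. The rule that a treated lesion is counted as permanently present works per lesion, so it does not move either. What changes is the number of interventions (planned Table 2.1.9 in SAP Appendix A) and whether study drug stops. Enrollment is about 10, so one participant classified differently moves the proportion stopping treatment by 1/10 = 10 percentage points.

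**The case against.** The strongest reply is that the sections can be read together. Section 8.2.4 could be taken to bar routine new therapy after drainage, with 6.6.2.1 governing true signs of infection. The reference to 6.6.2 in 8.2.4 and the exception in 6.6.3 point that way. The opposite reading is also available, with 8.2.4 as the specific rule that overrides the general one. Neither is written down, so the conflict stands. It is narrow: it needs drainage and then signs of infection after Week 4.

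On counting, the reply has more force. Two lesions at one visit, or one lesion at two visits, each give exactly 2 lesion-visits, which fits a trigger of more than 2. The and/or may mean different types on different lesions. Counts of 3 or 4 need the mixed reading, the third in the list above, which is possible but strained. A reader might infer that 8.2.4 contradicts itself; the text shows an ambiguity. The lesion count worksheet (Protocol Appendix D, SAP Appendix B), on which interventions are documented, was not in the text available for this review and may carry a counting convention.

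Three further inferences fail:

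- **That 2.2.1 grants antibiotics under 8.2.4.** It cites 6.6.2 jointly with 8.2.4, and infection can be read as belonging to 6.6.2. The cross-reference is untidy, since 8.2.4 mentions antibiotics only to prohibit them, and 2.2.1 is a rationale, not an operating rule.
- **That the lack of an antibiotic route before Week 4 is an inconsistency.** It is a restriction on which 6.6.2.1 and 6.6.3 agree.
- **That both rescue endpoints are affected.** Only the number of interventions is.

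**Conclusion.** The antibiotic conflict is real and is the main point: for a drained lesion with signs of infection after Week 4, the protocol gives opposite instructions and no precedence. The undefined intervention unit is secondary. It is an ambiguity that can turn a count of 2 into 3, and so a decision to continue into a decision to stop.

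The size is limited. The figure of 10 percentage points assumes 10 participants and one case; the documents give no expected frequency of rescue, of combined procedures or of infection after drainage. Efficacy is descriptive, with no formal hypotheses and no p-values, so no test result depends on this. The counting point also assumes that the worksheet appendix does not already define the unit. The reason to act is consistent care and consistent application of the stop rule across sites. No view is taken on which clinical rule is right.

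**What to change.** - Reconcile Protocol 8.2.4 with 6.6.2.1 and 6.6.3 on antibiotics for a drained lesion, so that all three carry the same rule, and align the cross-reference in 2.2.1 with the result.
- Reconcile the two paragraphs of 8.2.4 on whether injection and drainage of the same lesion at one visit are permitted.
- State in 8.2.4 what counts as one intervention, and use that unit for both the stop rule and the number-of-interventions endpoint in SAP 7.2. Check that the lesion count worksheet agrees.

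The cost is amendment wording in the protocol and a sentence in the SAP. The sample size and visit schedule do not change. The clinical content of each rule is for the sponsor to decide.

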8.2.5. Hidradenitis Suppurativa Pain Numeric Rating Scale

The HS Pain NRS (see Appendix F) will be completed in a daily diary by participants from screening through EOS. An 11-point scale will be used to assess the worst skin pain and the average skin pain due to HS. Ratings for the 2 items range from 0 (no skin pain) to 10 (skin pain as bad as you can imagine). Assessments will be recorded before bedtime or midnight (whichever comes first) and will be based on a recall period of the last 24 hours.

8.2.6. Analgesic Use

From screening through EOS, participants will complete a daily diary of their analgesic use (yes/no; see Appendix F). All analgesics and dose adjustments will be captured in the source and on the appropriate eCRF.

8.2.7. Hidradenitis Suppurativa Patient Global Impression of Change

Participants will complete the HS-PGIC questionnaire at the designated study visits listed in Table 3. The HS-PGIC consists of 1 self-administered item that assesses change in the severity of skin in the HS area. Participants are asked to indicate their impression of change compared with their last visit. The participant will answer the following: Since your last visit, your HS is: (1) very much improved, (2) much improved, (3) minimally improved, (4) no change, (5) minimally worse, (6) much worse, or (7) very much worse.

The participant should complete the questionnaire before site personnel perform any efficacy assessments.

8.2.8. Dermatology Life Quality Index

Participants will complete a DLQI questionnaire (see Appendix G) from screening through EOS. The DLQI will be used to assess the symptoms and the impact of skin problems on quality of life (Hongbo et al 2005). The DLQI can be used to evaluate 6 areas: symptoms and feelings, daily activities, leisure, work and school, personal relationships, and treatment. Participants will be asked to respond to the 10 items of the DLQI based on a recall period of "the last week." Decreased scores indicate improved health-related quality of life. The participant should complete the questionnaire before site personnel perform any efficacy assessments.

8.2.9. Photography of Target Lesions

For participants who consent to photography, a target area will be identified at screening and photographed for purposes of documentation. The lesion should be located in an area with inflammatory nodules and/or abscesses that are a good representation of the disease severity.

8.3. Safety Assessments

8.3.1. Adverse Events

Adverse events will be monitored from the time the participant signs the ICF until at least 28 days after the last dose of study treatment. Adverse events that begin or worsen after informed consent should be recorded on the Adverse Event Form in the eCRF regardless of the assumption of a causal relationship with the study drug. Conditions that were already present at the time of informed consent should be recorded on the Medical History Form in the eCRF. Adverse events (including laboratory abnormalities that constitute AEs) should be described using a diagnosis whenever possible rather than by individual underlying signs and symptoms.

Adverse events will be reported by the participant (or, when appropriate, by a caregiver, surrogate, or the participant's legally authorized representative). The investigator and any qualified designees are responsible for detecting, documenting, and recording events that meet the definition of an AE or SAE and remain responsible for following-up on AEs that are serious,

considered related to the study treatment, or that caused the participant to discontinue the study treatment. Care will be taken not to introduce bias when detecting AEs and/or SAEs. Open-ended and nonleading verbal questioning of the participant, such as "How are you feeling?" is the preferred method to inquire about AE occurrences. Adverse events may also be detected when they are volunteered by the participant during the screening process or between visits, or through physical examinations, laboratory tests, or other assessments. The definition, reporting, and recording requirements for AEs are described in Section 9.

All SAEs will be recorded and reported to the sponsor or designee within 24 hours. The investigator will submit any updated SAE data to the sponsor within 24 hours of it being available.

After the initial AE/SAE report, the investigator is required to proactively follow each participant at subsequent visits/contacts. All SAEs will be followed until resolution, stabilization, the event is otherwise explained, or the participant is lost to follow-up (as defined in Section 7.3).

8.3.2. Physical Examinations

Physical examinations will be conducted at the time points listed in Table 3.

A comprehensive physical examination will include height and body weight, and assessment of the following organ or body systems: skin; head, eyes, ears, nose, and throat; thyroid; lungs; cardiovascular system; abdomen (liver, spleen); extremities; and lymph nodes. A brief neurological examination will also be performed.

A targeted physical examination should be conducted as indicated by symptoms reported by the participant, AEs, or other findings. Abnormalities that are considered clinically significant in the judgment of the investigator are to be reported as AEs.

Physical examinations must be performed by a medically qualified individual such as a licensed physician, physician's assistant, or an advanced registered nurse practitioner, as local law permits.

8.3.3. Vital Signs

Vital sign measurements include blood pressure, pulse, respiratory rate, and body temperature. Blood pressure and pulse will be taken with the participant in the recumbent, semirecumbent, or sitting position after 5 minutes of rest. Any abnormalities that are considered clinically significant in the judgment of the investigator are to be reported as AEs.

8.3.4. Electrocardiograms

All 12-lead ECGs will be performed with the participant in a recumbent or semirecumbent position after at least 5 minutes of rest.

Electrocardiograms should be performed as indicated in Table 3. Additional 12-lead ECGs may be performed at other visits as deemed clinically necessary. Electrocardiograms will be interpreted by the investigator at the site, and the results will be used for immediate management of the participant's care. The decision to include or exclude a participant or withdraw a participant from the study based on an ECG flagged as "Abnormal, Clinically Significant" is the responsibility of the investigator, in consultation with the sponsor's medical monitor, as

appropriate. Any abnormalities that are considered clinically significant in the judgment of the investigator are to be reported as AEs.

Table 9: Electrocardiogram Schedule

	Timing of ECG Relative to Administration of Study Drug						
Study Visit	Not Applicable	Predose (trough) ECG ^a	Postdose ECG ^b				
Screening	Single → Triple						
Day 1		Triple ^c	Single → Triple				
Week 2			Single → Triple				
Week 6			Single → Triple				
Week 8 (EOT)		Single → Triple					

^a Predose ECG should be performed 5 to 10 minutes before the predose PK assessment.

